The course of TMS will occur as clinically determined by the TMS physicians providing the patient's care. The only unique aspect is that patients in the study will be randomized to either receive rTMS at the F3 location (determined using free software from clinicalresearcher.org) or the 5.5cm method, as is the current standard of clinical care at the University of Iowa for clinical rTMS treatments. Some early internal data has shown that these targets can vary anywhere from a few millimeters apart to a few centimeters, but all targets are within the prefrontal cortex on the left side and consistent with the FDA-approved treatment region for major depressive disorder. The nature of these targeting strategies

should prevent any target from ever falling outside a clinically approved range, but if for some reason it appears that a target is outside of the FDA-approved target region, a study physician will be called to evaluate and confirm the targeting, and adjust if felt to be clinically inappropriate (e.g., not in the prefrontal cortex for that patient). Noninvasive autonomic measures will be obtained during the course of treatment including blood pressure, heart rate, pupil size, and facial movements, although this should not interfere with or delay the administration of the TMS therapy. Some of these measures are already intermittently obtained on patients undergoing TMS therapy.

Treatment will then proceed as managed by the clinical rTMS service at University of Iowa. Follow-up appointments will occur as clinically scheduled by the rTMS clinical service and the patient's other providers as is standard of care. The patient and raters will be blinded to the treatment target for each patient, which will be assigned randomly. The treatment technician will be aware of the treatment site as needed for performing the appropriate measurements and targeting procedure during appointments.

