Title: The Effects of Repetitive Transcranial Magnetic Stimulation Prefrontal Target Location on  
Outcomes for Major Depressive Disorder

ID: 201709834

Date: 08/22/2019

rTMS Clinical Database (IRB ID#201709834)  
Data Analysis Plan

We will compare pre- and post-treatment rating scales, cognitive scores, and EEG/MRI results. Rating scales and cognitive/neurobehavioral scores will be analyzed using hypothesis-driven t-tests. iPad cognitive testing is normed to a US population adult control and results will be analyzed as T-statistics comparing the patients against a general population sample. A comparison of mean changes with confidence intervals and standard deviation calculations will be analyzed, as well as the difference in remission and response rates to treatment. For MRI we will compare structural volumetric changes, functional connectivity changes, T1rho pH changes, and DTI anisotropy changes.

Analysis pipeline is well established as mentioned above, with R package RnBeads and Minfi. We will control for standard demographics, including age, sex, race and psychotropic medication use known to affect DNA methylation status.

Audio recordings and their transcription are analyzed using a machine-learning algorithm to evaluate the predictive quality of vocal pattern detection and content value for treatment response to TMS.

Data received from IRB#201810778 will be used a comparison group for this study's heart rate variability data. Mean differences will be compared with t test statistics.

Based on previous work showing small efficacy differences between targets (31% remission with 5cm rule vs. 35% remission with certain Brodmann area targeting), power analysis with desired power of 0.80 and alpha of 0.05, we would need approximately 88 patients (44 in each group). We propose to recruit 200 patients.

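### The stated sample size (88 patients for 80% power on 31% vs 35% remission) is about 50-fold too small: 44 per group gives about 7% power, and the proposed 200 patients about 9%

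*SAP*

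**What the plan says.** The power statement is the last paragraph of the SAP's Data Analysis Plan, and neither document gives any other.

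- **Basis:** "Based on previous work showing small efficacy differences between targets", illustrated by "31% remission with 5cm rule vs. 35% remission with certain Brodmann area targeting".
- **Error rates and result:** "power analysis with desired power of 0.80 and alpha of 0.05, we would need approximately 88 patients (44 in each group"). Whether alpha is one- or two-sided is not stated.
- **Recruitment target:** "We propose to recruit 200 patients". Nothing links the 200 to a power, a dropout allowance or a subgroup.

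Earlier in the same plan, the difference in remission and response rates is listed as an analysis, with no test named. Rating scales are to be compared by t-tests, but no mean difference, standard deviation or standardised effect is given.

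The Protocol (Study Procedure Timeline and Protocol) says patients are "randomized to either receive rTMS at the F3 location" or by the 5.5cm method. It does not state the allocation ratio.

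**The concern.** A four-point difference between two proportions near one third cannot be detected with a few dozen patients per group. The required number should run to thousands, so 44 per group is implausible on sight.

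The claim matters because the target location is the one element of treatment that the trial randomises. If the true difference is the one assumed, the comparison will almost certainly be non-significant. A reader who accepts the stated 0.80 could then take that result as evidence that the two targets work equally well, when the trial could not have told them apart.

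A second, smaller problem lies in the same sentence. The planning rates compare a 5cm rule with Brodmann-area targeting, while the trial compares 5.5cm with F3. The SAP does not say that it is using the first comparison as a proxy for the second.

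**Working it through.** **Inputs**

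- From the SAP: p₁ = 0.31, p₂ = 0.35, power 0.80, alpha 0.05, 44 per group, 200 in total.
- Assumed: two-sided alpha (one-sided also tried), and 1:1 allocation of the 200 (100 per group), in line with the equal split of the 88.

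**1. Attempt to reproduce 44 per group**

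Pooled two-proportion formula, with p̄ = 0.33 and d = 0.04:

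n = [1.960·√(2·p̄(1−p̄)) + 0.8416·√(p₁(1−p₁) + p₂(1−p₂))]² / d²

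- First term: 1.960 × √0.4422 = 1.3033
- Second term: 0.8416 × √(0.2139 + 0.2275) = 0.8416 × √0.4414 = 0.5592
- n = (1.3033 + 0.5592)² / 0.0016 ≈ 2,168.05, so 2,169 per group and 4,338 in total
- Ratio to the stated figure: 4,338 / 88 = 49.3

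No standard variant comes close to 44:

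| Method | Two-sided n per group | One-sided n per group |
|---|---|---|
| Pooled | 2,169 | 1,708 |
| Unpooled | 2,166 | 1,706 |
| Arcsine | 2,168 | 1,708 |
| Continuity-corrected | 2,218 | 1,758 |
| Single sample against a fixed 31% | 1,070 | 845 |

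**2. Power actually delivered for 31% vs 35%**

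Under the normal approximation, power = Φ[(d − 1.96·SE₀)/SE₁] + Φ[(−d − 1.96·SE₀)/SE₁], where SE₀ = √(0.4422/n) and SE₁ = √(0.4414/n).

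- n = 44: SE₀ = 0.1002, SE₁ = 0.1002. Power = Φ(−1.562) + Φ(−2.361) = 0.059 + 0.009 = 0.068.
- n = 100: SE₀ = 0.0665, SE₁ = 0.0664. Power = Φ(−1.360) + Φ(−2.564) = 0.087 + 0.005 = 0.092.

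Other calculations of the same power:

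| Calculation | 44 per group | 100 per group |
|---|---|---|
| Exact enumeration, uncorrected two-sided z (chi-square) test | 7.3% | 9.3% |
| Fisher's exact test, two-sided | 4.3% | 6.8% |
| One-sided alpha 0.05, normal approximation | 10.6% | 14.8% |

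**3. What these sample sizes can detect (80% power, two-sided 0.05)**

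The confidence-interval half-width is 1.96·√(0.4414/n).

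| Analysed per group | Detectable remission vs 31% | Detectable standardised mean difference (t test) | 95% CI half-width at 31% vs 35% |
|---|---|---|---|
| 44 | 60.4% | 0.604 | 19.6 points |
| 100 | 50.3% | 0.398 | 13.0 points |

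At 100 per group the half-width is more than three times the assumed four-point effect (13.0/4 = 3.25).

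**4. Where 44 might have come from**

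A two-sample comparison of means needs 44 per group for a standardised difference of 0.60: 2 × (1.960 + 0.8416)² / 0.60² = 43.6, rounded up to 44. The SAP states no such effect, so this origin is conjecture.

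**5. Whether dropout explains the step from 88 to 200**

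It would imply losing 1 − 88/200 = 56% of patients. No dropout rate is stated.

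**The case against.** The strongest defence is that the 88 was never meant for remission. The SAP names no primary endpoint and no test for the power analysis, it plans t-tests for rating scales, and 44 per group fits a standardised mean difference of about 0.60. On that reading the fault is an effect size left out, not an arithmetic error. This softens the diagnosis but does not save the statement. The sentence bases the calculation on 31% and 35%, no mean difference or standard deviation appears anywhere, and a standardised difference of 0.60 does not fit a plan that calls the expected differences small.

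The SAP may also be an excerpt, since it refers back to text that is not there. No missing text could make 44 per group correct for 31% vs 35%.

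Four further points have some weight.

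- The trial plans 200 patients, so about 9% is the relevant power and about 7% describes a sample it does not intend to use.
- Neither document claims equivalence, and the SAP plans confidence intervals for mean changes. The risk of misreading is a risk, not something the plan asserts.
- Borrowing rates from a neighbouring comparison is ordinary practice, and the SAP already labels them by their targeting methods. Only the contrast with 5.5cm vs F3 is missing.
- Any restatement for 100 per arm is a best case. If, as an assumption, 20% of patients lack outcomes (80 per arm), the detectable remission rate rises to about 53%, the standardised difference to about 0.45 and the half-width to about 15 points. At 30% (70 per arm) the figures are about 54%, 0.48 and 16 points.

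**Conclusion.** The concern holds, and the SAP must be corrected. The stated sample size does not follow from the stated inputs: it is too small by a factor of about 49 at two-sided alpha and about 39 at one-sided alpha (3,416/88). The absence of a stated sidedness, test or allocation ratio does not change this, because every standard choice leaves the same conclusion. The 9% power for the planned 200 assumes 1:1 allocation and complete outcomes; unequal allocation or missing outcomes would lower it. The trial may have good exploratory reasons for recruiting 200 patients, but they do not make the 0.80 claim true. The mismatch between the planning comparison and the randomised one is a minor addition to this point.

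**What to change.** Delete the claim that 88 patients give 0.80 power and restate the paragraph for the 200 patients already proposed. Suggested wording:

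> With 100 patients analysed per arm (1:1 allocation, two-sided alpha 0.05), the trial has 80% power to detect 31% vs about 50% remission, or a standardised difference of 0.40 in mean scale change. Power for 31% vs 35% is about 9%. The remission difference will be reported with its 95% confidence interval, expected to be about ±13 percentage points, and a non-significant result will not be interpreted as equal efficacy. The 31% and 35% rates come from a comparison of a 5cm rule with Brodmann-area targeting, not from 5.5cm vs F3.

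If the sponsor expects missing outcomes, the figures should be given for the number expected to be analysed. If the 88 was in fact calculated for a rating scale, the SAP should name that scale and state the mean difference and standard deviation assumed.

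The cost is SAP wording only, with no added patients, procedures or changes to treatment. The stated power becomes less favourable.
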